
Objectives:
 
Primary objective: To demonstrate that the protease inhibitor nelfinavir, administered orally to SLE subjects with mild to moderately active disease, will decrease serum anti-dsDNA autoantibody binding by $\geq 35\%$.
 
Secondary objectives: 1) To assess the safety and tolerability of nelfinavir in SLE patients, 2) To assess the effect of nelfinavir on serum cytokine levels (IL-1, IL-6, and TNFα), 3) To assess the effect of nelfinavir on serum levels of C3, C4 and CRP, 4) To assess the effect of nelfinavir on the interferon signature, 5) To assess the effect of nelfinavir on binding of anticardiolipin antibodies, 6) To demonstrate that nelfinavir does not increase lupus disease activity and 7) To demonstrate that nelfinavir decreases disease activity.

Hypothesis:
 
Nelfinavir, a well-tolerated drug used to treat HIV, will be efficacious as a lupus therapeutic through inhibition of anti-dsDNA antibody binding to target organs and possibly through interfering with the formation of pro-inflammatory, DNA containing immune complexes, pro-inflammatory cytokines, and the IFN signature.

Study Arms:
 
A maximum of forty-three evaluable subjects will be required to assess the objective response rate ($>35\%$ reduction in dsDNA reactivity at 8 wks – end of treatment).
 
Stage 1: (maximum of 13 subjects enrolled)
 
 • If 3 or fewer respond, the trial is stopped due to an inadequate response rate • If 4 or more subjects respond, the trial continues to Stage 2 
Stage 2: (maximum of 30 additional subjects enrolled)
 
 • At end of Stage 2, if 12 or fewer of the 43 subjects respond, the treatment is declared inadequate • If 13 or more respond, then the treatment will be considered for further testing

Study Design:
 
This is an exploratory, multicenter, Phase IIa clinical trial with no placebo arm that utilizes the Simon Two-Stage trial design to investigate the immunomodulatory properties of nelfinavir, a protease inhibitor, in SLE patients with mild to moderate disease activity and elevated titers of anti-dsDNA antibodies. The safety, tolerability, and preliminary assessment of efficacy of nelfinavir in SLE patients will be explored.


Study Population: Subjects must meet the following criteria:
 
Inclusion Criteria:
 
 1. Subject is capable of providing written informed consent 2. Subject is ≥ 18 years old and ≤ 65 years old 3. Meets at least 4 of 11 modified American College of Rheumatology (ACR) (1997) Revised Criteria for the Classification of Systemic Lupus Erythematosus 4. Has mild to moderate disease activity defined as 
 • A minimum SLEDAI score of 2 excluding points for serology (anti-dsDNA antibody and complement) • No active renal or nervous system disease • No BILAG A in any organ system • No expectation by the investigator that corticosteroids will need to be added or doses increased during the 8 week treatment period for any reason • No expectation by the investigator that immunosuppressive medication will need to be added or doses increased during the 8 week treatment period

Title of Protocol: Nelfinavir in Systemic Lupus Erythematosus – A Pilot Phase IIa Clinical Trial

5. Has elevated titers of anti-ds DNA antibody at the time of screening (defined as the titer that meets
Meets criteria for “high” in the Core Laboratory at the North Shore/LIJ Health System; unequivocal high titer as opposed to borderline, indeterminate or intermediate)
6. Has elevated titers of cross-reactive anti-DNA/DWEYS antibodies at the time of screening (the assays for anti-DNA/DWEYS antibodies will be performed in Dr. [name]’s laboratory; study sites will be notified of results within 3 days of receipt of the samples).
7. If on glucocorticoids, the dose must be $\leq 10\text{mg}$ daily and stable or decreasing 4 weeks prior to baseline
8. If on immunosuppressive or immunomodulatory medication such as azathioprine, methotrexate, leflunomide, mycophenolate, belimumab or hydroxychloroquine, the dose must have been stable for the 3 months prior to screening, and expected to remain stable over the course of the study.
9. Males and females with potential for reproduction must agree to practice effective birth control measures (2 approved methods of contraception). Nelfinavir can decrease serum levels of oral contraceptives; the slightly increased risk of pregnancy due to an interaction between oral contraception and nelfinavir will be discussed when appropriate and the requirement for a second approved method of contraception will be addressed.

Exclusion Criteria:

1. Current or prior treatment with rituximab or anti-CD22 monoclonal antibody in the 12 months prior to this study or any other biologic agent for 90 days prior to this study
2. Treatment with cyclophosphamide within the 6 months prior to screening
3. Increase in glucocorticoid dose within 4 weeks of screening or addition of a DMARD in the three months prior to study
4. A history of drug or alcohol abuse within the 6 months prior to screening
5. Elevated LFT’s:
 - ALT or AST ≥ 2 x upper limit of normal at screening
 - serum unconjugated bilirubin $> 3\text{mg/dL}$ at screening
6. Dialysis or serum creatinine $> 1.5\text{mg/dL}$
7. Hypercholesterolemia: total cholesterol $> 230\text{ mg/dL}$ or LDL $> 150\text{ mg/dl}$ or hypertriglyceridemia (triglyceride $> 200\text{mg/dL}$) at screening
8. Laboratory/clinical evidence of: pancreatitis: amylase/lipase $> 3\text{x}$ upper limit of normal at screening
9. Known current/active infections including HIV, Hepatitis B, Hepatitis C
10. History of cancer, excluding skin cancers (squamous cell or basal cell that have been treated)
11. Known active tuberculosis or untreated tuberculosis
12. Hemoglobin $< 8\text{ g/dL}$
13. Expectation by the investigator to increase corticosteroid or immunosuppressive, or immunomodulatory medication dose at screening, baseline, or over the course of the study
14. Pregnancy or lactation
15. Consumption of > 2 cups of grapefruit juice per day
16. Treatment with medications metabolized using the cytochrome P3A4 pathway, such as cyclosporine, tacrolimus, gemfibrozil, niacin, itraconazole, ketoconazole, erythromycin, azithromycin, clarithromycin, bosentan, nefazodone, tricyclic antidepressants
17. Treatment with any drugs known to interact with nelfinavir that include amiodarone, quinidine, midazolam, triazolam, ergotamine, dihydroergotamine, methylergonovine, pimozide, lovastatin, simvastatin, rifampin, St. John’s Wort, aluzosin, cisapride and sildenafil.
18. Any condition that, in the opinion of the Investigator, would jeopardize the subject’s safety following exposure to the study drug.

Endpoints:

Primary endpoint: inhibition of anti-dsDNA binding (based on titers from baseline to Day 56).

Secondary endpoints: a) **Safety:** frequency of adverse events, b) **Disease Activity:** this study will evaluate the potential effect of nelfinavir on different assessments of disease activity from baseline to Day 56, including SELENA SLEDAI, BILAG, Joint count, PGA, SLICC Damage Index, Lupus PRO, patient global assessment, c) **Interferon Signature:** changes in expression of IFN inducible genes (from baseline to Day 56), and d) **Cytokines:** changes in serum cytokine levels (from baseline to day 56).

Sample Size: A maximum of 13 subjects will be enrolled in Stage 1 and a maximum of an additional 30 subjects will be enrolled in Stage 2 for a total of 43 evaluable subjects.

INVESTIGATOR SIGNATURE PAGE

Protocol Title: Nelfinavir in SLE: A pilot phase IIa clinical trial

Protocol Version: Version 07.17.17

Study Sponsor: The Feinstein Institute for Medical Research

Funding Agency: National Institute of Arthritis and Musculoskeletal and Skin Diseases (NIAMS)

Please print, sign, and date at the indicated location below. A copy should be kept for your records and the original signature page sent to [name], Study Coordinator, at the Feinstein Institute for Medical Research.

I confirm that I have read the above protocol in the latest version. I understand it, and I will work according to the principles of Good Clinical Practice (GCP) as described in the United States Code of Federal Regulations (CFR) – 21 CFR Parts 45, 50, 56, and 312, and the International Conference on Harmonization (ICH) document “Guidance for Industry: E6 Good Clinical Practice: Consolidated Guidance” dated April 1996. Further, I will conduct the study in keeping with local, legal, and regulatory requirements.

As a Principal Investigator on this protocol, I agree to conduct the study “Nelfinavir in SLE: A pilot phase IIa clinical trial” by the criteria written in the protocol and understand that no changes can be made to this protocol without written permission of the NIAMS (funding agency) and the Feinstein Institute for Medical Research (sponsor).

Principal Investigator (Print)

Principal Investigator Signature

Date

IND 114834; Sponsor: [name], FIMR, NS-LIJHS

Title: Nelfinavir in Systemic Lupus Erythematosus: a pilot phase IIa clinical trial

1. INTRODUCTION

The overall goal of purpose of this exploratory Phase IIa clinical trial will be to investigate the immunomodulatory properties of nelfinavir, a protease inhibitor (PI) that is approved by the Food and Drug Administration (FDA) for treatment of Human Immunodeficiency Virus (HIV) disease, in Systemic Lupus Erythematosus (SLE). Specifically, we will determine the safety, tolerability and obtain a preliminary assessment of the efficacy of nelfinavir in patients with SLE that have mild to moderate disease activity and elevated titers of cross-reactive anti-dsDNA/anti-DWEYS peptide (anti-DNA/DWEYS) antibodies. The clinical trial is accompanied by mechanistic studies designed to investigate the *in vivo* effects of nelfinavir on anti-dsDNA antibody binding, interferon inducible genes (the IFN signature) and circulating cytokines in the in peripheral blood.

The hallmark of SLE is autoantibody production; anti-dsDNA antibodies in particular are highly specific for SLE. They have been eluted from kidney and brain tissue and are associated with disease severity and activity [1-2]. Deleterious effects of anti-dsDNA antibodies are mediated by direct binding to tissue substrate and formation of immune complexes that incite inflammatory responses through toll-like receptor (TLR) signaling, complement activation and Fc receptor binding. Anti-dsDNA antibodies are known to cross-react with protein epitopes, in particular with a DWEYS pentapeptide consensus sequence that appears in the N-Methyl D-Aspartate receptor (NMDAR) in brain and kidney. These cross-reactive anti-DNA/DWEYS antibodies contribute to lupus neuro- and nephrotoxicity and synthetic *d*-DWEYS peptide blocks pathogenic autoantibody binding *in vitro* and ameliorates kidney and brain complications in lupus models [3]. Certain PIs used for treatment of HIV disease may share a structural motif that is similar to that found in the DWEYS peptide. Preliminary *in vitro* ELISA studies in our lab have demonstrated that some of the PIs (nelfinavir, atazanavir, lopinavir, saquinavir, ritonavir, indinavir, and darunavir) can inhibit binding of a murine monoclonal anti-dsDNA antibody (R4A antibody) to DWEYS peptide, dsDNA and C1q (section 2.3). We have also demonstrated that one of the PIs, nelfinavir, inhibits binding of anti-dsDNA antibodies from lupus patients sera to dsDNA. These results have led us to hypothesize that one or more of the PIs may have beneficial effects in SLE through effects on anti-dsDNA antibody binding to antigen in addition to effects on pro-inflammatory cytokines and other inflammatory molecules such as high mobility group box protein 1 (HMGB-1). Current treatments of SLE include cytotoxic medications and treatment options that have a safer toxicity profile are urgently needed. PIs are currently used for treatment of HIV disease and are generally well-tolerated. Nelfinavir was chosen for use in this clinical trial because it has fewer potential side effects than the other PIs tested. We hypothesize that nelfinavir may have beneficial effects in the treatment of SLE through inhibition of anti-dsDNA antibody binding to target organs and, perhaps, through interfering with the formation of pro-inflammatory, DNA-containing immune complexes, pro-inflammatory cytokines and the IFN signature.

The planned clinical trial utilizes a Simon Two-Stage “optimal” trial design [4]. It will be conducted at the Feinstein Institute for Medical Research (FIMR) of the North Shore-LIJ Health System (NS-LIJ HS) and at least 7 other clinical sites. The clinical trial will be overseen by Drs. [name] and [name] who co-direct the Clinical Research Unit in the Center for Autoimmune and Musculoskeletal Disease at the FIMR. [name], head of the Center for Autoimmune and Musculoskeletal Disease, will also collaborate on this project and will be responsible for conducting the mechanistic studies.

The primary objective of this clinical trial is:

- To demonstrate that the protease inhibitor nelfinavir, administered orally to SLE subjects with mild to moderate disease activity, will decrease serum anti-dsDNA antibody binding by $\geq 35\%$.

Secondary, exploratory objectives are:

- To assess the safety and tolerability of nelfinavir in SLE patients.
- To assess the effect of nelfinavir on serum cytokine levels (IL-1, IL-6, and TNF α).
- To assess the effect of nelfinavir on serum levels of C3, C4 and CRP.
- To assess the effect of nelfinavir on the interferon signature.
- To assess the effect of nelfinavir on binding of serum titers of anticardiolipin antibodies.
- To demonstrate that nelfinavir does not increase lupus disease activity.
- To demonstrate that nelfinavir decreases disease activity.

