The Simon Two-Stage trial design limits exposure to study drug that is not effective and we believe that this trial design provides an efficient method for assessment of an FDA approved medication for HIV disease for another purpose. This study design does not have a placebo arm; all subjects will be dosed with nelfinavir 750 mg orally thrice daily. If the thrice daily dose is not tolerated, subjects will be allowed to decrease the dose to twice daily. For both stages of the trial the dosing period is 8 weeks followed by a 4 week observation period. A maximum of 13 subjects will be enrolled in the first stage of the trial followed by a maximum enrollment of an additional 30 in the second stage. The primary endpoint or "Response" is defined as a $\geq 35\%$ reduction in serum anti-dsDNA antibody titer from baseline values to end of treatment (8 weeks). This definition is based on established changes in anti-dsDNA titers in other lupus trials. We will test the null hypothesis that the true objective Response rate is $\leq 20\%$ (Inadequate Response Rate, which would not be clinically meaningful) versus the alternative hypothesis that the true Response rate is $\geq 40\%$ (Desirable Target Response Rate, Figure 5). Importantly, these Response Rates are consistent with results from other lupus clinical trials (e.g., immunosuppressives, steroids) where $\leq 20\%$ was considered not significant and $\geq 40\%$ was clinically meaningful. With a significance level of 0.05 and a power of 0.80, a maximum of 43 evaluable subjects (13 in Stage 1 plus 30 in Stage 2) will be required to assess the objective Response rate (Figure 5) [4]. From among the 13 subjects enrolled in Stage 1; if 3 or fewer objective Responses are observed, then the trial will be terminated (Figure 5A). If 4 or more objective Responses are observed in the first 13 subjects, however, the study will be expanded to enroll an additional 30 patients (Stage 2; Figure 5B). At the end of the study, if 13 or more Responses are observed, then the null hypothesis that the true response probability is $\leq 20\%$ will

be rejected and further investigation of nelfinavir in this patient population is warranted (Figure 5B) [4].

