This study is exploratory and is not powered to adequately assess efficacy. However, we plan to enroll subjects with mild to moderate disease activity that, in the investigators opinion, will not require additional corticosteroids or immunosuppression for treatment of their disease activity. Five different assessments of disease activity are planned therefore we anticipate that we will be able to detect a trend for efficacy in those treated with nelfinavir. The potential effect of nelfinavir on clinical indicators of disease will be evaluated descriptively. Clinical indicators of disease will include:

- Changes in serum C3 and C4 complement levels from baseline to Day 56;
- Changes in serum CRP from baseline to Day 56;
- Changes in the SELENA SLEDAI score from baseline to Day 56;
- Changes in the PGA from baseline to Day 56;
- Changes in from baseline to Day 56;
- Changes in Joint Count from baseline to Day 56;
- Changes in BILAG scores from baseline to Day 56.

c) Health related quality of life

The potential effects of nelfinavir on patient quality of life will be assessed by changes in patient reported outcome measures from baseline to Day 56. The quality of life measures for this clinical trial include the following:

- The LupusPro Health Survey is a validated patient reported measure of functional health and well-being generalizable across ethnic backgrounds and gender [37].
- The patient global assessment scale is a 10 cm visual analogue scale with 1 mm increments from 0 through 100. 0 reflects no disease activity in the patient's assessment and 100 reflects maximum disease activity.

d) Interferon signature

Secondary analyses will explore the potential effect of nelfinavir on the expression of the IFN signature. Changes in expression of IFN inducible genes will be determined from baseline to Day 56. Expression of IFN inducible genes will be determined in two ways:

- Transfer of the IFN signature: as described previously [38], serum from SLE subjects will be incubated with normal PBMC and expression of IFN inducible genes will be measured using reverse transcriptase PCR.
- Microarray analysis: Expression of IFN inducible genes in peripheral blood will be measured by microarray analysis of RNA (extracted from whole blood in the PaxGene tubes) using the Illumina HT12v4 platform.

e) Cytokines

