6. STUDY WITHDRAWAL OR DISCONTINUATION

6.1 Discontinuation of Protocol-Specified Treatment Requirements

A subject is considered to have completed the study when he/she has completed the Day 84 visit. Protocol-specified requirements for the treatment of subjects will be discontinued for subjects under the following conditions:

1. Any protocol-specified treatment requirement will be discontinued immediately at any time during the study at the request of the subject.
2. Investigator will discontinue any protocol-specified treatment requirement if the subject's health, safety, and/or well-being is threatened.
3. Protocol-specified treatment requirements will be discontinued and replaced with appropriate therapy for any subject who experiences or requires any of the following:
 - An increase in dose of any concurrent SLE medications (including but not limited to corticosteroids, immunosuppressives, and/or immunomodulatory medications such as azathioprine, methotrexate, leflunomide, mycophenolate, and/or hydroxychloroquine) or addition of a new immunosuppressive medication (including cyclophosphamide or rituximab). *Note:* corticosteroids may be increased for a maximum of 2 days for reasons unrelated to SLE disease activity provided the last dose is taken more than 5 days prior to the day 56 assessments (section 5.3)
 - A grade 3 or higher NCI-CTCAE (version 4.0) adverse event that is considered to be related to study therapy during the course of the study. The exception to this will be hemoglobin levels where a grade 3 level of 8 may be acceptable. This will depend on the hemoglobin level at study entry and the investigator's assessment of relationship to study drug. A requirement for blood transfusion would be considered a stopping point.
 - Pregnancy
 - If a subject enrolls in a concurrent interventional trial.

In addition, subject non-compliance with treatment regimens or failure to keep appointments may disrupt protocol-specified treatment requirements and necessitate permanent discontinuation of treatment procedures at the discretion of the investigator.

Finally, protocol specified treatment requirements will be discontinued as a natural consequence in subjects who are withdrawn from the study per the study guidelines.

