6.1.1 Procedures for Discontinuation of Protocol –Specified Treatment Requirements and Follow-Up

For subjects who have been discontinued from protocol-specified treatment requirements but have not withdrawn consent, the following procedures will apply:

1. The subject will be asked to complete a discontinuation visit at the time of study discontinuation that will include a physical exam, lupus disease assessments as applicable (SLEDAI, BILAG, joint count), SLICC, LupusPRO, PGA, cbc, chemistry, C3, C4, anti-dsDNA and mechanistic studies.
2. If discontinuation is due to safety concerns, the subject will be given appropriate care under medical supervision, until the symptoms of any adverse event resolve or the subject's condition becomes stable.

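### Objectives 6 and 7 promise to demonstrate effects on disease activity, but the uncontrolled Day 56 change scores have no rule or population for subjects who stop because lupus treatment was increased

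*Combined protocol and SAP*

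**What the plan says.** **Objectives.** The synopsis (secondary objectives 6 and 7) and section 1 both contain "To demonstrate that nelfinavir does not increase lupus disease activity" and "To demonstrate that nelfinavir decreases disease activity". The other five secondary objectives are only to assess something. Section 1 introduces the list with "Secondary, exploratory objectives are".

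**Design and analysis.** Section 5.1 states: "This study design does not have a placebo arm". Section 5.4.2(b) states: "This study is exploratory and is not powered to adequately assess efficacy". It plans description only and defines the SELENA SLEDAI, PGA, joint count and BILAG endpoints as changes from baseline to Day 56. For these measures the plan gives no margin, test, confidence interval, missing-score rule or analysis population.

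**Stopping treatment.** Under section 6.1, protocol treatment ends for a subject who needs "An increase in dose of any concurrent SLE medications". Short corticosteroid increases for reasons other than SLE are permitted (sections 5.3 and 6.1). Section 6.1.1 then provides: "The subject will be asked to complete a discontinuation visit at the time of study discontinuation". That visit covers SLEDAI, BILAG and joint count as applicable, plus SLICC, LupusPRO and PGA. No later visit is mentioned.

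**Safety side.** Section 5.4.2(a) also judges safety by disease activity. Section 8.1 grades flares from new BILAG scores. Section 7.1.1 keeps every dosed subject in the adverse-event analyses, including those who are replaced.

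**SLICC.** The synopsis endpoints, assessed from baseline to Day 56, include "Joint count, PGA, SLICC Damage Index, Lupus PRO, patient global assessment".

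**The concern.** Objective 6 is a no-harm statement. It needs a definition of worsening and a population that includes the subjects who worsened. The listed endpoints supply neither: they need a Day 56 score, and the subjects most likely to lack one are those whose lupus led to more treatment. Objective 7 is tilted in the same direction, because an average over those who reached Day 56 looks better than an average over everyone dosed.

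With no control arm, even a complete set of change scores could not separate a drug effect from the natural course of a disease that section 2.1 describes as one of recurrent flares. At stake is a statement in the trial report that nelfinavir was shown not to aggravate lupus, or to improve it, resting mainly on subjects who did not need more treatment.

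**Working it through.** **1. The plan's own figures.** These concern only the primary anti-dsDNA endpoint. With stage rules 3/13 and 12/43, exact binomial sums give:
- at a 20% response rate: type I error 0.0496, early termination 0.747, expected N = 13 + (1 − 0.7473) × 30 = 20.58;
- at a 40% response rate: power 0.8002.

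These agree with section 7.1 (0.05, 75%, 20.6 and 0.80). No corresponding figure exists for disease activity.

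**2. The path of a subject who worsens.**
- Section 6.1: SLE medication is increased for lupus, so treatment stops.
- Section 6.1.1: one discontinuation visit, with activity scores.
- Section 5.4.2(b): the endpoint is the Day 56 score minus baseline.
- No section links the discontinuation score to that endpoint, or schedules a Day 56 visit after treatment stops.

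**3. Size of the tilt in the mean (illustration).** The documents give no SD or flare rate. Assumptions: true mean change zero, normal changes, the worst fraction q by need for treatment has no Day 56 score, and 43 subjects remain. If need for treatment has correlation ρ with the change score, the shift towards improvement is ρ × φ(z)/(1 − q) SD, where z is the upper-q normal point. For q = 10%: 0.1755/0.90 = 0.195 SD at ρ = 1, and half that at ρ = 0.5. The last two columns give the chance that a two-sided 95% CI falsely shows a decrease (20,000 simulated trials per case); it is 2.5% when nothing is missing.

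| q | Shift, ρ = 1 | Shift, ρ = 0.5 | False decrease, ρ = 1 | False decrease, ρ = 0.5 |
|---|---|---|---|---|
| 5% | 0.109 SD | 0.054 SD | 11% | 5% |
| 10% | 0.195 SD | 0.097 SD | 30% | 9% |
| 15% | 0.274 SD | 0.137 SD | 59% | 15% |
| 20% | 0.350 SD | 0.175 SD | 86% | 21% |

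For comparison, the 95% CI half-width without bias is 0.31 SD at n = 43 and 0.60 SD at n = 13.

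**4. Size of the tilt in a proportion (illustration).** Assume 51 dosed (the maximum in section 7.1.1), 43 completers of whom 3 worsen, and k of the other 51 − 43 = 8 leaving for added SLE treatment. Exact (Clopper-Pearson) 95% intervals:
- completers only: 3/43 = 7.0% (1.5 to 19.1);
- all dosed, k = 0: 3/51 = 5.9% (1.2 to 16.2);
- all dosed, k = 5: 8/51 = 15.7% (7.0 to 28.6);
- all dosed, k = 8: 11/51 = 21.6% (11.3 to 35.3).

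**5. What even a perfect result would show.** With no worsening among n subjects, the exact 95% upper limit is 1 − 0.025^(1/n): 8.2% at n = 43 and 24.7% at n = 13.

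**6. SLICC.** In section 5.4.1 it is on the Day 1 list but not on those for Days 28, 56 or 84. Section 6.1.1 adds it at discontinuation. A subject who completes treatment therefore has one value and no change. This needs no assumption.

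**The case against.** Several points on the other side stand.

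- A reader might infer that every subject who worsens is lost. The documents do not say so. Stopping treatment (6.1) is separate from withdrawal (6.2), and only withdrawal expressly ends visits and data collection. A Day 56 visit after stopping is neither scheduled nor ruled out. Worsening first recognised at Day 56 has a score.
- A reader might infer that harm would stay hidden. It need not. Section 5.4.1 calls for a new SELENA SLEDAI at an unscheduled visit when activity has changed and the last one is more than 10 days old. Discontinuation visits record scores, a new BILAG A is reported in an expedited manner (8.4.1), and flares stay in the all-dosed safety data. What is missing is a statement that objective 6 will be answered from those data.
- A reader might infer a completer-only analysis from section 7.1.1. Its replacement and exclusion rule is written for the Simon evaluation. For the activity summaries the population is simply undefined.
- A reader might infer that subjects chosen for current activity will improve anyway. Entry sets a floor (SLEDAI of at least 2) but also ceilings: no BILAG A and no active renal or nervous system disease. The documents do not settle the net direction.
- The objectives are labelled exploratory, and no decision rule depends on them. That limits the consequence, but it also makes the verb harder to defend.

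**Conclusion.** The point holds as a mismatch between wording and design, together with an undefined population and missing-score rule. As written, the Day 56 summaries can selectively omit subjects who worsened, and the resulting bias is favourable. Its size cannot be known from the documents. The figures of 0.05 to 0.35 SD for 5% to 20% missing rest on the assumptions in the working, as do the proportions. The missing control arm is a separate limit that no handling of scores removes. The SLICC gap is certain: under the visit lists, no completer has a change.

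The primary Simon decision is untouched, and worsening is recorded elsewhere in the trial. This is an inexpensive improvement that should be made, not a flaw that undermines the trial.

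**What to change.** 1. **Objective 6.** In all dosed subjects, report with an exact 95% CI the proportion who, by Day 56, have a new BILAG A or B, or an increase or addition of SLE medication for lupus activity. Do not count the short non-SLE corticosteroid increases permitted in sections 5.3 and 6.1.
2. **Change scores.** Beside the Day 56 summaries, add one in all dosed subjects that uses the discontinuation-visit score when there is no Day 56 score, and state how many subjects have neither. The patient global assessment is not named on the section 6.1.1 list, so it may have no substitute value.
3. **SLICC.** Remove it from the Day 56 change endpoints in the synopsis and report it at baseline.
4. **Wording.** Change objectives 6 and 7, in the synopsis and section 1, to *estimate* the proportion who worsen and *describe* the change. State that without a control arm neither can be attributed to nelfinavir.

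The cost is edits to the synopsis and sections 1 and 5.4.2, plus one or two tables from data already collected. No visit, sample size or treatment rule changes. The downside is that the worsening figure may look less favourable and the clinical claims become more modest.
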